- 7. Subject has a history of any malignancy.
- 8. Subject is known to be human immunodeficiency virus positive or had other known immunodeficiency.
- 9. Subject has any clinically significant laboratory test abnormalities or a history of any other condition that, in the opinion of the Investigator, could compromise the subject's ability to comply with the protocol or that could compromise the subject's safety or the interpretation of the study results.
- 10. Subject is currently participating in any other therapeutic clinical study.
- 11. Subject is pregnant or lactating.

Statistical Analysis:

Part 1 and Part 2 will be analyzed in a similar fashion with the exception that the Part 1 analysis will include a sample size evaluation. Part 1 analyses in some instances may be confined to the descriptive aspect of the evaluation (i.e., inferential p-values may be omitted) due to the small sample size of 6 treated and 3 control patients.

The primary efficacy endpoint (VIIS scaling severity as assessed by the Investigator in the target efficacy area) as well as all secondary efficacy variables that are captured on a continuous or semi-continuous

scale

will be expressed as baseline to ending change scores. Two-sided 95% confidence intervals (CIs) will be computed and used descriptively for all variables but also to evaluate change relative to a standard for some variables (i.e., by determining whether the CI includes or excludes the standard).

The two-sided 95% CI for VIIS scaling severity will be used to evaluate the primary endpoint as follows. An efficacy claim from Part 2 will be made if: 1) the lower confidence interval is above zero, 2) the midpoint of the confidence interval is at least 0.5 units is size, and 3) at least 50% of subjects have favorable change scores of one or greater.

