10.1 Sample Size

Part 1 of the study will assess the effect size on the VIIS scaling severity score with ADX-102 1% topical dermal cream, and will confirm the sample size needed for Part 2. Part 2 is expected to require approximately 30 subjects.

The approximate number of 30 subjects for Part 2 was based on the NS-003 Phase 2 study which used the ISS endpoint. The mean ISS Scaling sub-score change from baseline was -0.7 with a standard deviation of 0.52. Conservatively, the change was set to -0.5 and the standard deviation to 0.6. A sample size of 20 achieves 94% power to detect a difference of 0.5 between the null hypothesis mean of 0.0 and the alternative hypothesis mean of -0.5 with an estimated standard deviation of 0.6 and with a significance level (alpha) of 0.05 using a two-sided one-sample t-test. If the above assumptions remain, except that the standard deviation is increased to 0.7, then a sample size of 20 achieves a power of 85%. The sample size of 30 is therefore based on these estimates requiring 20 subjects to be treated with ADX-102 1%. As subjects will be randomized in a 2:1 ratio, 10 subjects will be treated with vehicle.

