10.1. PRIMARY EFFICACY ENDPOINT AND ANALYSIS

The primary endpoint for the clinical trial is change from baseline in the VIIS scaling score in drug-treated subjects, as assessed by the investigator, in the target efficacy area. The VIIS provides five-point Likert scales (range 0-4) for erythema and scaling that increases in severity with increasing score values.

The target efficacy area for all efficacy analyses will be one of the body sites as defined in the VIIS tool (with the exception of Dorsal foot) with Grade 2 or higher on baseline VIIS scaling score as assessed by the Investigator.

The within-group change from baseline will be the primary focus of interest in the primary analysis.

Syneos Health #1009367

Primary Analysis

A Mixed Model Repeated Measures (MMRM) model will be used to perform the primary analysis of the VIIS scaling score in drug-treated subjects (not vehicle-treated subjects). Change from baseline VIIS scaling score will serve as the dependent variable. The model will include the baseline value (Visit 1) as a covariate (if useful) and visit (treated as a factor; the visit term will cover Visit 1, 5, 7, and 8). An unstructured covariance structure will be assumed and a Type III model will be evaluated. If the unstructured covariance structure matrix results in a lack of convergence, then Toeplitz (TOEP), first-order autoregressive (AR1), compound symmetric (CS) covariance structure will be used in that order. If the MMRM model cannot hit convergence with any correlation structure, then a within-subject t-test (baseline-adjusted, if useful) will be used to compare baseline to Visit 8. It should be noted that improvement will be signified by the existence of a negative change score.

The primary efficacy endpoint will be summarized descriptively by visit and across all visits. The table will contain descriptive statistics on observed values and change from baseline at each time point.

The primary analysis using the MMRM model will be summarized in a consolidated table containing the following:

- Descriptive statistics for change scores at baseline and each post-treatment time point.
- The LS mean change scores with accompanying standard errors and 95% confidence intervals for each visit.
- Within-group contrasts for each given visit.
- Significance levels for the visit effects.

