Along with the table detailing the results of the MMRM model, a consolidated table presenting the essential information for the primary analysis will be constructed. The primary endpoint will be deemed to have been met if the Visit 8 (week 24) term is significant, and the term coefficient is negative.

Secondary and Sensitivity Analyses Related to the Primary Outcome Variable

The following analyses will be performed to provide additional insight into VIIS scaling.

Responder Analysis

For drug-treated subjects, responder status will be assigned to a subject if at a given post treatment time point an improved change from baseline of at least 1 VIIS scaling

Syneos Health #1009367

unit occurs. A Generalized Estimating Equation (GEE) model will be used to evaluate the predicted log odds, odds and probability of response. The model will include the effect of visit (treated as a factor). An unstructured covariance structure will be assumed and a Type III model will be evaluated. If the unstructured covariance structure matrix results in a lack of convergence, then first-order autoregressive (AR1) and compound symmetric (CS) covariance structure will be used in that order.

Results will be captured in a consolidated table that contains the following information:

- Number and percent of observed responders and non-responders at all post-treatment time points;
- Significance levels for the visit effects;
- The model predicted log odds, odds and probability of response with standard errors and 95% confidence intervals for each visit;
- Within-group contrasts expressed as an odds ratio, accompanied by a 95% confidence interval.

AUC Analysis

For drug-treated subjects, AUC for change from baseline over all post-treatment time points will be calculated for each subject using the trapezoidal rule. A linear model comparing AUC to zero (no change from baseline) will be performed.

Survival Analysis

For drug-treated subjects, time to first response (i.e., a one-unit VIIS scaling improvement) will be captured in a Kaplan Meier plot. A hazard rate estimate will be generated.

Analysis for Patients Experiencing one or more Treatment interruptions

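### SAP 10.1 replaces a non-converging unstructured model with equal-variance structures, so in about six subjects the Part 1 Visit 8 success test can exceed its nominal error rate

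*SAP*

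**What the plan says.** The primary model in SAP 10.1 covers drug-treated subjects only. The Protocol synopsis (Statistical Analysis) expects inference in Part 1 to be limited "due to the small sample size of 6 treated and 3 control patients". The response is change from baseline in VIIS scaling, a 0-4 whole-grade scale. Visit is a factor, and "the visit term will cover Visit 1, 5, 7, and 8". For the covariance, "An unstructured covariance structure will be assumed and a Type III model will be evaluated". On non-convergence the order is fixed: "then Toeplitz (TOEP), first-order autoregressive (AR1), compound symmetric (CS) covariance structure will be used in that order". Only if every structure fails does the plan reach its last step: "then a within-subject t-test (baseline-adjusted, if useful) will be used to compare baseline to Visit 8".

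The Part 1 endpoint is "deemed to have been met if the Visit 8 (week 24) term is significant, and the term coefficient is negative". SAP 10.1 gives no alpha and no degrees-of-freedom method for that term. The nearest statement is in Protocol 10.1, where the Part 2 size was set "with a significance level (alpha) of 0.05 using a two-sided one-sample t-test".

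**The concern.** Toeplitz, AR(1) and compound symmetry, as named, each have a single variance parameter. No heterogeneous version is listed. Under any of them the standard error of the Visit 8 mean is not based on the spread at Visit 8. It comes from a variance pooled over all modelled visits. If Week 24 changes vary more than earlier ones, that standard error is too small and the test rejects too often. If they vary less, the test is conservative.

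The success rule rests on this one term, so whether Part 1 is declared met can depend on which structure happened to converge. The test that does not pool, the Visit 8 t-test, is already in the plan. It sits behind three structures that all have to fail first.

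**Working it through.** **Inputs.** From the documents: n = 6 treated; response visits 1, 5, 7 and 8 (baseline, Weeks 12, 20, 24); whole-grade scores 0-4; two-sided 0.05 (Protocol 10.1, taken over as an assumption for SAP 10.1). Assumed, because not given: visit-specific SDs, correlations between visits, complete data, no baseline covariate, and the Visit 8 term read as the Visit 8 mean change tested against zero.

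**The plan's own figure.** Protocol 10.1 powers a one-sample t-test with n = 20 and difference 0.5. Noncentrality is 0.5 × √20 / 0.6 = 3.73 on 19 df, giving 94.2% (stated: 94%). At SD 0.7 it is 3.19, giving 85.8% (stated: 85%). Both reproduce. That reference test uses the SD of one change score, with no pooling over visits.

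**How the pooling acts.** With complete data and compound symmetry, the squared standard error of the Visit 8 mean is (average of the visit variances) / n. The t-test uses (Visit 8 variance) / n. For SD ratios a : b : c at Weeks 12, 20 and 24, the standard error is therefore off by the factor √[(a² + b² + c²)/(3c²)]. Example: 0.6 : 0.8 : 1 gives √[(0.36 + 0.64 + 1)/3] = √0.667 = 0.82. With Visit 1 rows (variance zero) and equal SDs afterwards, it is √[(0 + 1 + 1 + 1)/4] = √0.75 = 0.87.

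**Error rate by simulation.** Null data, normal, 6 subjects, REML fits of the three structures, Satterthwaite df (between-within df also run), two-sided 5%:

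| SD ratio, Weeks 12 : 20 : 24 | SE factor (CS) | Two-sided error |
|---|---|---|
| 1 : 1 : 1 | 1.00 | 4.8-5.4% |
| 0.8 : 0.9 : 1 | 0.90 | 7.0-7.5% |
| 0.7 : 0.85 : 1 | 0.86 | 8.0-9.0% |
| 0.6 : 0.8 : 1 | 0.82 | 9.2-10.3% |
| 0.5 : 0.75 : 1 | 0.78 | 10.9-12.5% |
| 1 : 0.85 : 0.7 | 1.23 | 1.8-2.3% |
| Visit 1 rows in, equal SDs after | 0.87 | 8.9-10.4% (CS, AR1) |

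If the whole doubling falls after Week 20 (0.5 : 0.5 : 1), the error is 14-17%. The Visit 8 t-test stayed at 4.4-5.5% in every pattern. Success also needs a negative coefficient, so false success is about half: under Toeplitz 2.5% at equal SDs and 5.0% at 0.6 : 0.8 : 1, against a nominal 2.5%. With n-1 = 5 df the inflation is smaller, with two-sided error of roughly 3-8%.

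**How often the fallback is reached.** With Visit 1 in the response, every subject's change there is zero, so the unstructured matrix is singular by construction. With Visit 1 left out and null scores rounded to whole grades, it was singular in 21-76% of trials when the Week 24 SD before rounding was 0.6 (the protocol's planning SD), and in 6-33% when it was 0.8. Counting only those singular trials, the fallback's two-sided error was 5.5-9.1% with equal SDs and 8.8-14.5% with rising SDs. Over all trials, the unstructured-then-Toeplitz sequence on rounded scores (10 df) rejected in about 4% with equal SDs, 6-7% with moderate rises and 9-12% with steep rises.

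**A worked case.** Three of six subjects improve one grade at Visits 7 and 8, and one of those three had already improved at Visit 5. The Visit 7 and Visit 8 columns are identical, so the matrix has rank 2 and the unstructured model has no finite fit.

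- Visit 8: mean -0.5, variance (6 × 0.25)/5 = 0.30, t = -0.5/√(0.30/6) = -2.24, 5 df, p = 0.076.
- Compound symmetry: visit variances 0.167, 0.30, 0.30, average 0.256, t = -0.5/√(0.256/6) = -2.42. With 10 df p = 0.036; with 5 df p = 0.060.
- Toeplitz, the structure the SAP would use first: p = 0.031 with 10 df, 0.054 with 5 df. AR(1): 0.033 and 0.057.

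The same data meet the endpoint or miss it, depending on the pooled variance together with the unstated degrees of freedom.

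**The case against.** A reader might infer that the fallback simply runs at 9-10%. The documents do not support that. With Visit 1 excluded it takes a Week 12 SD of only about 0.6-0.65 of the Week 24 SD, and no section gives SDs by visit. SAP 8.2 and 10.2 describe SLS symptoms as persistent and not improving on their own, and the target area is treated from Week 1, so a marked rise in spread between Weeks 12 and 24 is possible but not shown. That stands, and it is why the size is given as a range.

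The worked reversal needs the larger degrees of freedom as well as the pooled variance: with 5 df all three structures agree with the t-test. That also stands, and it is a reason to state the method. Naming Satterthwaite would not be a cure, because the table already uses it.

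Rank deficiency is a proxy for the SAP's trigger, which is non-convergence. What the software would report, or what the optional baseline covariate would do, was not tested.

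A reader might also infer that the efficacy claim is at risk. It is not. This SAP covers Part 1 (section 2). Protocol 10 and 10.4 rest the claim on Part 2 alone, and the start of Part 2 depends on safety, a mean change near 0.5 and feasibility, not on this p-value. SAP 8.2 treats significance as a supplementary index and allows small-sample substitutes. These points lower the severity. They do not remove the fault: SAP 10.1 still sets a formal success rule, SAP 8.3 says the primary analysis is inferential, and the substitution in 8.2 is discretionary and made after seeing the data.

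**Conclusion.** Wrong as written; moderate severity. The fallback order puts three equal-variance structures ahead of a Visit 8 test that holds its level. With Visit 1 excluded and within-subject or Satterthwaite df, the fallback's two-sided error is about 5% for equal SDs, about 7-12% when the SD rises gradually by a quarter to double by Week 24, and below 5% when it falls. With Visit 1 rows in the model, the fallback is certain and the error is about 9-10% even with equal SDs at Weeks 12-24. On the success rule's own one-directional scale, each figure is about halved and compares with 2.5%.

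The sizes rest on assumed SD patterns and correlations, normal scores (whole-grade where stated), complete data and no baseline covariate. The mechanism does not: it follows from the structures named. The consequence is confined to the Part 1 success statement.

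**What to change.** In SAP 10.1:

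1. Limit the response visits to 5, 7 and 8. Visit 1 enters only as the baseline value.
2. Remove the Toeplitz, AR(1) and compound-symmetry steps. If the unstructured model cannot be fitted, go directly to the Visit 8 one-sample t-test on change from baseline with n-1 df. Alternatively, list only heterogeneous-variance structures ahead of that t-test.
3. State two-sided alpha 0.05 for the Visit 8 term, and Kenward-Roger or n-1 df for the unstructured model.

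This changes SAP wording only. The cost is that, in the t-test fallback, a subject with no Visit 8 value does not contribute. That matters with about six treated subjects and no imputation (SAP 8.5). The heterogeneous-variance option would keep such a subject's earlier visits in the model.

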3. STUDY OVERVIEW

ADX-103-SLS-006 is a multicenter, randomized, double-blind, vehicle-controlled, parallel-group Phase 3 clinical trial to evaluate the safety and efficacy of ADX-102 1% topical dermal cream in subjects with Sjögren-Larsson Syndrome (SLS).

This is a two-part clinical trial, with an initial assessment of increasing BSA treatment (Part 1). After the completion of Part 1, a separate set of eligible subjects will be enrolled into Part 2.

Subjects 3 years of age or older with genetically-confirmed diagnosis of SLS and active ichthyosis are eligible for enrollment. For detailed inclusion and exclusion criteria, see Section 4.1 and 4.2 in the protocol, version 5.0.

Part 1 Design:

Part 1 will evaluate the safety, tolerability, and efficacy of treatment to the affected area of ichthyosis initially on approximately 20% BSA and then increasing up to 90% BSA over 24 weeks of exposure and will confirm an appropriate sample size for Part 2.

Subjects will be consented and screened for eligibility. Approximately nine subjects will be randomized in a 2:1 ratio to receive ADX-102 1% or vehicle.

Subjects or caregivers will apply study drug (i.e., ADX-102 1% or vehicle) to a treatment area identified by the Investigator.

The initial treatment area will be defined as approximately 20% BSA with Grade 2 or higher on the Visual Index for Ichthyosis Severity (VIIS) scaling score, as assessed by the Investigator, and will include one of the body sites as defined in the VIIS tool (target efficacy area). From Week 1 through Week 12, subjects will receive treatment once daily in the initial treatment area only.

If the Investigator determines that there are no safety or tolerability issues at the end of Week 12, the treatment area will increase to all of the affected areas of ichthyosis on one-half of the body (approximately 40-45% BSA in a typical SLS patient). From Week 13 through Week 20, subjects will receive treatment once daily on the expanded treatment area.

If there are still no safety or tolerability issues at the end of Week 20, the treatment area will further increase to all affected areas of ichthyosis on the entire body (approximately, 80-90% BSA in a typical SLS patient). Subjects will receive treatment once daily treatment on all affected areas from Week 21 through Week 24.

Subjects completing the 24 weeks of study drug treatment will then be monitored for an additional four weeks for safety.

Syneos Health #1009367

Part 2 Design:

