10. EFFICACY

Overview

All efficacy variables are initially captured on a continuous or semi-continuous scale. Observed values at the time of collection and change from baseline value at each time point will be summarized descriptively. Mixed Model Repeated Measures (MMRM) analysis will be carried out on change from baseline scores for the primary and secondary efficacy variables for reproxalap-treated subjects (not vehicle-treated subjects). Hereinafter, in this Statistical Analysis Plan, drug-treated shall mean reproxalap-treated. Additional analyses in drug-treated subjects will be performed on certain efficacy variables. Further details of the tests to be performed on each endpoint are given in Table 10.2.1 below. The specific additional analyses are described below.

- 1) The VIIS outcomes will be converted to a binary response variable (yes/no) defined as a 1-unit and 2-unit improvement from baseline. The probability of response in drug-treated subjects will be analyzed over time using generalized estimating equation (GEE) models.
- 2) Change from baseline over time will be converted into an Area Under the Curve (AUC) value using the trapezoidal rule. AUC for drug-treated subjects will be inferentially compared to zero (0 = no change from baseline) using a linear model.
- 3) Time to first response (1-unit improvement and 2-unit improvement) for the VIIS outcomes (scaling and erythema) will be evaluated using a Kaplan Meier survival curve for drug-treated subjects.

Tables will be generated for each endpoint presenting appropriate descriptive and inferential statistics to convey the results of the analyses. Tables will be augmented by figures for selected analyses.

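### The Part 1 responder GEE compares visits with one another rather than testing efficacy, and it breaks down at any visit where none or all of about six drug-treated subjects respond

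*SAP*

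**What the plan says.** Part 1 is small. In SAP 3, "Approximately nine subjects will be randomized in a 2:1 ratio to receive ADX-102 1% or vehicle". The protocol synopsis (Statistical Analysis) notes that p-values may be omitted "due to the small sample size of 6 treated and 3 control patients".

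Under Responder Analysis in SAP 10.1, a drug-treated subject is a responder at a post-treatment time point on "an improved change from baseline of at least 1 VIIS scaling" unit. The overview in SAP 10 lists response "defined as a 1-unit and 2-unit improvement from baseline" for the same type of model. The method is: "A Generalized Estimating Equation (GEE) model will be used to evaluate the predicted log odds, odds and probability of response". On the mean model the SAP says "The model will include the effect of visit (treated as a factor"). No treatment term, vehicle comparison or reference rate is given.

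The output table is to hold:
- "Number and percent of observed responders and non-responders at all post-treatment time points";
- p-values for the visit effects;
- model-based log odds, odds and probability for each visit, with standard errors and 95% intervals;
- "Within-group contrasts expressed as an odds ratio, accompanied by a 95% confidence interval".

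If the unstructured covariance does not converge, AR1 and then compound symmetry are tried. The primary MMRM in the same section names its visits (1, 5, 7 and 8). The GEE names none. VIIS is also scheduled at Visit 2 (Day 2).

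**The concern.** Response is itself a change from baseline, so the response rate at baseline is zero by construction and no odds ratio against baseline exists. With visit as the only factor, the visit test and the odds ratios can only ask whether the response rate moves between post-treatment visits. A drug that produces a high, stable response, which is the hoped-for result, earns no significance. A reader of the Part 1 report could take a non-significant visit effect as absence of benefit, or a significant one as proof of it. Neither follows.

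With six subjects, 0/6 or 6/6 at a visit is a realistic outcome. A logit model with a separate level for each visit then has no finite estimate for that visit. The specified fallback acts on non-convergence and changes only the working covariance, so it addresses a different problem. At stake is a Part 1 table that prints a spurious p-value or an interval with no meaning.

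**Working it through.** **Figures in the plan.** Neither document gives an operating figure for this GEE. The only stated design calculation is the Part 2 one-sample t-test in Protocol 10.1 (n = 20, difference 0.5). It gives 94% power at SD 0.6 and 85% at SD 0.7. Exact noncentral-t values are 94.2% and 85.8%, so it reproduces. It does not bear on the responder model.

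**Inputs.** n = 6 drug-treated subjects (protocol synopsis). Visits 5, 7 and 8 are the later site visits with VIIS. True response rates are not given, so 50%, 67% and 80% are assumed. The 67% has some support: Protocol 10.1 reports a Phase 2 mean change of -0.7 with SD 0.52, and four one-point improvers among six give mean -4/6 = -0.67 and SD = sqrt[(4 × 0.333² + 2 × 0.667²)/5] = 0.52. That is an inference, and it comes from the ISS, not the VIIS.

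**1. What is tested.** Logit GEEs with a visit factor were fitted to example data for six subjects.
- The same 5/6 responding at all three visits: log odds ln(5/1) = 1.61 at each visit, and the visit test gives p = 1.0 under independence and unstructured working correlation. The exchangeable fit failed.
- 4/6, 4/6, 5/6: log odds 0.69, 0.69, 1.61; visit p = 0.41.

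Both patterns show most subjects improved, and neither gives a small p-value. The test is not aimed at that question.

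**2. What happens at 0/6 or 6/6.**
- 4/6, 5/6, 6/6: log odds 0.69, 1.61 and then 24 to 30, depending on where iteration stopped. The fit reported convergence, SE 0.41 for the degenerate visit and a visit p below 1e-120.
- 0/6 at Day 2, then 4/6, 4/6, 5/6: log odds of about -24 to -30 at Day 2, again reported as converged, with a visit p of effectively zero.
- Independence, exchangeable and unstructured all behaved this way. Because convergence was reported, the AR1/CS fallback would not be triggered. Changing the working correlation would not make the estimate finite either.
- The other visits kept their usual values (for 4/6, log odds 0.69 with SE 0.87).

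**3. How often.** For one visit, P(0/6 or 6/6) = p⁶ + (1-p)⁶. For three independent visits, P(at least one) = 1 - (1 - that value)³. Correlated visits were simulated with an equicorrelated latent normal.

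| True response | One visit | Any of three, independent | Any of three, latent correlation 0.9 |
|---|---|---|---|
| 50% | 3.1% | 9% | 6% |
| 67% | 9% | 25% | 16% |
| 80% | 26% | 60% | 39% |

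The formula is symmetric, so a 20% rate, which might apply to the 2-unit responder, gives the same 39-60%.

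**4. If Day 2 is modelled.** P(0/6 at Day 2) = (1-d)⁶, where d is the Day 2 response rate. The documents do not give d. The result is 100% at d = 0, 94% at 1%, 74% at 5%, 53% at 10% and 38% at 15%.

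**5. Exact alternative.** Clopper-Pearson 95% intervals for n = 6 are bounded at every count: 0/6 gives 0% to 46%, 4/6 gives 22% to 96%, 6/6 gives 54% to 100%.

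**The case against.** Several points on the other side stand.

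- The analysis is secondary, offered as added insight into scaling, and SAP 10 describes it as response probability over time. A visit-only model does describe that. SAP 8.2 also says that significance levels are a supplementary index rather than something the trial is expected to achieve.
- The same table gives observed counts and percentages, so the response rate is reported whatever the model does. A degenerate visit spoils its own estimate and any test or contrast that uses it, not the estimates at other visits. A reader might infer that the analysis will often yield nothing. The documents do not support that.
- A reader might infer that failure is near certain because VIIS is taken on Day 2. That needs two things the documents do not supply: a Day 2 response rate close to zero, and a statement that Day 2 enters the model. The wording about all post-treatment time points belongs to the observed counts. The MMRM visit list, the m-ITT requirement for a VIIS after Visit 2, and the exploratory pooling of Visits 5, 7 and 8 (SAP 10.4) all suggest that Day 2 may be left out. For the central-reader version no photograph is scheduled on Day 2.
- SAP 8.2 allows small-sample methods to be substituted, with a rationale, if the data warrant it. This is a partial answer: it is discretionary, is exercised after the data are seen, and names neither a trigger nor a method for 0% or 100% response.

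None of this makes the visit p-values informative about efficacy, or makes the 0/6 and 6/6 output valid.

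**Conclusion.** The concern holds in two parts. First, the visit p-values and within-group odds ratios compare post-treatment visits and carry no evidence of efficacy. This follows from the model as written and needs no assumption. Second, the model has no finite estimate at a visit with none or all responding, the stated fallback does not repair it, and software may print a convincing but spurious result. With Visits 5, 7 and 8 only, the chance of at least one such visit is about 6-9%, 16-25% and 39-60% at true response rates of 50%, 67% and 80%. These assume six evaluable subjects, a constant rate across visits and latent correlation from 0.9 down to 0. Above 50%, the risk rises as the response rate rises. It is higher again if Day 2 is modelled.

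Because the Part 2 claim rule includes a responder percentage, a reader might infer that the claim is threatened. It is not: that rule uses an observed proportion, this SAP covers Part 1, and Protocol 10.4 rests the efficacy conclusion on Part 2 data. The consequence is confined to how a secondary Part 1 analysis is read. It should be corrected, but it does not undermine the trial.

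**What to change.** In SAP 10.1, under Responder Analysis:
- State that the analysis covers Visits 5, 7 and 8.
- Report n/N responders with exact (Clopper-Pearson) 95% intervals at each visit, for each arm, as the responder result.
- Delete the visit-effect p-values and the visit odds ratios.
- If the GEE is kept as a description over time, pre-specify that its estimates and tests are not reported when any modelled visit has 0% or 100% response.

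Apply the same wording to central-reader scaling, which Table 10.2.2 assigns the same analysis, and to any 2-unit version.

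The cost is a change of SAP wording and simpler programming. It fits SAP 8.3, which already plans descriptive statistics for the secondary endpoints. The loss is that there would be no single repeated-measures model for response. The exact intervals will be wide, which is an honest reflection of six subjects.
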